2.1 MAIN OBJECTIVES, PRIMARY AND SECONDARY ENDPOINTS

2.1.1 Main objectives

The primary objective of this study is to objectively describe cough frequency, utilizing four 24-hour cough recordings over 12 weeks in a cohort of subjects with Non IPF Pulmonary Fibrosis or IPF using the cough monitor.

The secondary objectives for this study are:

- Assess the relationship between objective cough frequency and FVC (mL)
- Assess feasibility of patient performed remote cough data upload
- Assess feasibility of hybrid study design (% successful completion of remote visits)

2.1.2 **Primary endpoint(s)**

Primary Endpoints: Cough count per hour (CC/hr) measured over a 24-hour period at baseline visit, Week 4(V4), Week 8(V5), Week 12 (V6).

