Subsequently, interval history will be obtained, followed by video-assisted supervised home spirometry with the site study team. Immediately following the end of the study visit, the patient will initiate a 24-hour cough count recording. At completion of 24 hrs. of recording the next day, the patient will remove the sensor from their chest wall and place the sensor onto a charger to allow for data upload via Bluetooth connected app on the study-provided mobile phone. The charger will be placed next to the study provided mobile phone, which is "pre-loaded" with the place app, to allow for data upload. The sensor will be charged for the next visit and stored as per vendor instructions until the next recording at Visit 6. The site study team will confirm that the prior 24-hour cough recording was completed and offer to assist the patients with any part of the 24-hour cough recording that they were having trouble with.

Visit 6- Remote

Visit 6 will occur on the 82nd day (-2 days) prior to the EoS visit. On the day of the study visit, the patient is asked to complete home spirometry (Visit 6) via logon to the platform for video supervision by a spirometry trained member of the site study team. Immediately following the end of the study visit, the patient will initiate a 24-hour cough recording. At completion of 24 hrs. of recording the next day, the patient will remove the sensor from their chest wall and place the sensor onto a charger to allow for data upload via Bluetooth connected app on the study-provided mobile phone. The charger will be placed next to the study provided mobile phone, which is "pre-loaded" with the provided app,

Proprietary confidential information © 2022 Boehringer Ingelheim International GmbH or one or more of its affiliated companies

to allow for data upload. Once data upload is complete, the sensor and study provided phone will be stored for return to the site at the EoS visit (Visit 7).

Visit 7 – On site

The End of Study Visit (EoS/V7) will occur on the 84th day (+/- 5 days) following study enrollment/baseline visit.

Interval history will

be obtained; vital signs and a physical exam will be performed. Participants will then undergo spirometry on-site.

The and home spirometry devices will be returned to the site as will the provisioned mobile phone.

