4. CHANGES IN THE PLANNED ANALYSIS OF THE STUDY

For the endpoint "Cough frequency and number of cough bouts at each of the activity levels (exertion): stationary/low, medium/high", activity levels will be categorized as:

- Low activity
- Medium activity
- High activity

"Stationary" activity represents non-wear time.

Only inspiratory crackles will be summarized for the endpoint "Lung sound events (potentially including, but not limited to, inspiratory crackles)

5. **ENDPOINTS(S)**

5.1 **PRIMARY ENDPOINT(S)**

The primary endpoints as stated in the CTP are: Cough count per hour (CC/hr) measured over a 24-hour period at baseline visit, Week 4(V4), Week 8(V5), Week 12 (V6).

Note that these endpoints are the average CC/hour at each of the 4 visits.

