The % of analysable data per 24-hour recording period will be derived from the cough count recording times(Total readable recording time) and defined as:

Total readable recording time

24 (hours)

- x 100

Descriptive statistics will be produced by visit as well as the number and percentage of patients who have $\geq 80\%$ (19.2 hrs) of analyzable data.

• Feasibility of hybrid study design (successful completion of all elements of remote visit)

Successful completion of a remote visit will be based on the questions on the home study procedures eCRF:

- Was home spirometry performed? (Visit 3, Visit 4, Visit 5, Visit 6)
- Was the videoconference televisit completed? (Visit 4, Visit 5)
- Was the 24 hour cough recording completed? (Visit 3, Visit 4, Visit 5)

The number and percentage of patients who complete each element will be tabulated by visit as well as the number an percentage of patients who complete all elements by visit.

Correlation analyses:

Sample Spearman and Pearson correlation coefficients for the pairs of CC/hr and FVC measurements listed above along with the associated p-values to assess the relationship between objective cough frequency and FVC (mL), correlations will be calculated. Scatter plots for the pairs of variables will also be produced.

Boehringer Ingelheim

 TSAP for BI Trial No: 1490-0005
 Page 19 of 27

 Proprietary confidential information © 2024 Boehringer Ingelheim International GmbH or one or more of its affiliated companies

001-MCS-50-415_RD-01 (3.0) / Saved on 18 Jan 2021

Boehringer Ingelheim TSAP for BI Trial No: 1490-0005

Proprietary confidential information © 2024 Boehringer Ingelheim International GmbH or one or more of its affiliated companies

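### SAP 7.5.2 omits the 24-hour recording from Visit 6, so the Visit 6 all-elements completion rate reduces to home spirometry and can overstate feasibility

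*SAP*

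**What the plan says.** Protocol 2.1.1 makes feasibility a secondary objective: "Assess feasibility of hybrid study design (% successful completion of remote visits". The matching endpoint in Protocol 2.1.3 and SAP 5.2.2 requires every element of the remote visit to be completed.

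SAP 7.5.2 turns this into a rule: "Successful completion of a remote visit will be based on the questions on the home study procedures eCRF". Three questions follow, each with its own visit list:

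- home spirometry, at Visits 3, 4, 5 and 6;
- videoconference, at Visits 4 and 5;
- the recording: "Was the 24 hour cough recording completed? (Visit 3, Visit 4, Visit 5".

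Each element, and completion of all elements, is then tabulated by visit.

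On where the recordings take place, the two documents agree:

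- The protocol flow chart marks the recording and its upload at Visits 2, 4, 5 and 6. Footnote 11 has the recording start as soon as the remote visit ends.
- Protocol 6.1, under Visit 6, says: "Immediately following the end of the study visit, the patient will initiate a 24-hour cough recording".
- Protocol 6.1, under Visit 5, has the sensor "stored as per vendor instructions until the next recording at Visit 6".
- SAP 5.1 defines the primary endpoint as "Cough count per hour (CC/hr) measured over a 24-hour period at baseline visit, Week 4(V4), Week 8(V5), Week 12 (V6", and SAP Table 6.7:1 marks Visit 6 as remote.

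**The concern.** The recording is one of the two things the patient has to do at Visit 6, and it supplies the Week 12 cough data. The printed scoring rule leaves it out, so the Visit 6 all-elements rate is simply the home spirometry rate under another name.

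The error runs one way, in favour of the design being tested. Protocol 1.3 says that a successful hybrid design could be carried into Phase 2 and 3 trials, so this percentage may be used for planning. A reader who follows the rate across Visits 4, 5 and 6 could also take a rise at Visit 6 for better adherence when it came from the definition.

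The visible text of SAP section 4, which lists changes to the planned analysis, declares no change to this endpoint.

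**Working it through.** The plan states no figure for this endpoint, so there is none to reproduce. The check compares element lists and then works out the direction and size of the difference.

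**Step 1. Elements per remote visit** (S = home spirometry, T = videoconference, R = 24-hour recording). The protocol column comes from the flow chart and section 6.1, the SAP column from the lists in 7.5.2.

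| Visit | Protocol | SAP as printed | Scheduled elements scored |
|---|---|---|---|
| 3 | S | S, R | 1 of 1, plus one not scheduled there |
| 4 | S, T, R | S, T, R | 3 of 3 |
| 5 | S, T, R | S, T, R | 3 of 3 |
| 6 | S, R | S | 1 of 2 |

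**Step 2. Direction at Visit 6.** Let N be the number of patients in the denominator.

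- Printed rate = n(S) / N
- Protocol-defined rate = n(S and R) / N
- Difference = D / N, where D = n(S and not R)

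D cannot be negative, so the printed rate is never below the protocol-defined one. They are equal only if everyone who does Visit 6 spirometry also makes the recording.

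**Step 3. Size.** Take N = 50, the planned number of patients. Each patient counted in D adds 100 / 50 = 2 percentage points. D is not known; the values below are arithmetic only.

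| D | Overstatement (points) |
|---|---|
| 0 | 0 |
| 1 | 2 |
| 3 | 6 |
| 5 | 10 |

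**Step 4. Does another reading of the three items rescue the text?** Protocol 6.1 has a look-back at Visit 5: "The site study team will confirm that the prior 24-hour cough recording was completed". The Visit 3 item could likewise be a look-back to the baseline recording, which finishes the day after Visit 2. The flow chart's compliance check, marked at Visits 3 to 6, also names cough recordings.

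| Reading of the listed visits 3, 4, 5 | Remote recordings left unscored |
|---|---|
| Literal: the recording of that visit | Visit 6 |
| Visit 3 item looks back to Visit 2; the others are literal | Visit 6 |
| All look back (3 to 2, 4 to 2, 5 to 4) | Visits 5 and 6 |
| Slip for Visits 4, 5, 6 | None, but the SAP text is wrong |

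While the list stands as printed, no reading reaches the recording started at Visit 6. Only a slip removes the bias, and a slip needs correcting.

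**Step 5. What other outputs show.** The by-element table uses the same visit lists, so as printed it has no Visit 6 recording row. The analysable-data endpoint is summarised by visit ("Descriptive statistics will be produced by visit as well as the number and percentage of patients who have" at least 80% analysable data), so Week 12 recording yield is partly visible there. Missing values are not imputed, however, so a patient with no recording may drop out of its descriptive statistics. That table also does not give spirometry and recording jointly.

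**The case against.** The strongest counter-argument is that the list paraphrases an eCRF page that the documents do not include. If that page has a Visit 6 recording item, or the list is off by one visit, the table may come out right and the reported bias is zero. The unchanged endpoint definition in SAP 5.2.2 makes a slip plausible. This stands as a limit on what can be said about the results. It does not defend the SAP text, which is wrong or unclear on every reading.

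Four further points have some force:

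- **Comparability.** Visits 4 and 5 include a videoconference and Visit 6 does not, so the rates would differ in content even after the fix. That is correct. The fix makes each rate cover all that its own visit schedules; it does not make the visits identical.
- **Recovery.** Protocol 7.2.1 has all individual data listed, and the number of Week 12 cough values will be reported. The joint Visit 6 figure could be rebuilt by hand. What is missing is the pre-specified summary, not the data.
- **Denominator.** Two points per patient needs exactly 50 patients. The protocol says about 50 evaluable, and the SAP uses the Entered Set, whose size is not given. The general figure is 100/N points.
- **Weight.** The study is exploratory, without hypotheses, and the visible text sets no success threshold for this endpoint. That caps the importance, but the rule for a stated secondary objective is still misdefined.

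**Conclusion.** The concern holds. As printed, SAP 7.5.2 scores one of the two elements scheduled at Visit 6, so at least one of the four remote visits is mis-scored under the printed rule. The resulting rate can overstate completion and cannot understate it. The size is 2 points per affected patient if N = 50; the number of affected patients is unknown and may be none.

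Confidence is high about the text. Whether the reported figure would be biased depends on the eCRF. The Visit 3 item needs only clarification, since it is plausibly a look-back to the baseline recording. The primary endpoint, the change-from-baseline analyses and the correlations are not affected. It should be fixed, but it does not threaten the study's main results.

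**What to change.** First reconcile the SAP's visit lists with the eCRF and the protocol flow chart. Then:

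- Add the Visit 6 recording to the Visit 6 all-elements rule. Use the eCRF item if there is one. Otherwise derive it from the recording-time or upload data already used for the analysable-data endpoint, and state what counts as completed.
- Footnote the source of the Visit 6 item.
- Say which recording the Visit 3, 4 and 5 items refer to. Do not count a look-back to the baseline recording as a Visit 3 procedure unless the SAP says so.

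The cost is a line of SAP wording and, if the eCRF has no Visit 6 item, a simple derivation from data already collected. There are two downsides. The Visit 6 rate may look less favourable. And if Visit 6 comes from device data while Visits 4 and 5 rest on the eCRF question, the sources differ, which is why the footnote is needed.

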3.3 SELECTION OF STUDY POPULATION

The study population will include subjects (aged 18 and above) with Non IPF Pulmonary Fibrosis (defined as \geq 10% fibrosis on high resolution Chest CT as per principal investigator assessment) or IPF who are residing in one of the target countries and follow the routine clinical practice of the participating sites. We will target enrolment of 25 subjects with Non IPF Pulmonary Fibrosis and 25 with IPF.

Screening of patients for this study is competitive, i.e. screening for the study will stop at all sites at the same time once a sufficient number of patients has been screened. Investigators will be notified about screening completion and will then not be allowed to screen additional patients for this study. Patients already in screening at this time will be allowed to continue to enrollment if eligible.

A log of all patients enrolled into the study (i.e. who have signed informed consent) will be maintained in the Investigator Site File (ISF) irrespective of whether they chose to complete the study or not.

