3.3.1 Main diagnosis for study entry

The study population will include subjects (aged 18 and above) with Non IPF Pulmonary Fibrosis or IPF, who are residing in one of the target countries. The study population will be enriched (70% of study population) for persons with clinically significant cough at the Screening Visit, defined as having

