7.2.4 Secondary objective analyses

Secondary endpoints will be summarized descriptively by visit.

Change from baseline in CC/hr at Week 4, Week 8, and Week 12 will be summarized in terms of absolute changes in CC/hr and in terms of geometric mean ratios. Model based estimates for changes from baseline at Week 12, for example least squares means adjusted for baseline CC/hr or other covariates, may be calculated.

Standard descriptive statistical parameters will be tabulated for all other secondary endpoints.

To assess the relationship between objective cough frequency and FVC (mL), correlations (spearman and Pearson) will be calculated between the following variables:

- Baseline CC/hr (log-transformed) and Baseline FVC (mL)
- Baseline CC/hr (log-transformed) and FVC (mL) at Week 12
- Baseline CC/hr (log-transformed) and change from baseline FVC (mL) at Week 12
- CC/hr at Week 12 (log-transformed) and FVC (mL) at Week 12
- Change in CC/hr at Week 12 (calculated from log-transformed values) and change from baseline in FVC (mL) at Week 12

Graphical presentations of the secondary endpoints and correlations may also be produced. Further details will be included in the SAP.

Page 41 of 71

Proprietary confidential information © 2022 Boehringer Ingelheim International GmbH or one or more of its affiliated companies

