7.5 DETERMINATION OF SAMPLE SIZE

[P22-04417] was a phase 2a study which investigated the effect of inhaled RVT-1601 (cromolyn sodium) on 24-hour average cough counts in patients with IPF. 97 patients were randomized to four arms (RVT-1601 10mg, 40mg, 80mg, or placebo for 12 weeks). The baseline measurements of the mean 24-hour cough count were 38.0 ± 26.6 (RVT-1601 10mg; n=27); 36.8 ± 21.7 (RVT-1601 40mg arm; n=22); 35.7 ± 17.8 (RVT-1601 80mg arm; n=23); 34.3 ± 19.6 (Placebo; n=25).

Assuming we observe similar standard deviations for cough count as the SCENIC trial, the table below reports the 95% confidence interval range we expect for the 24-hour cough count assuming a sample size of 50 patients that are normally distributed. For example, when the sample size is 50, a two-sided 95% confidence interval for a mean will extend 7.484 from the observed mean, assuming that the standard deviation is known to be 27 and the confidence interval is based on the large sample z-statistic.

Table 7.5: 1 Confidence Interval ranges based on N=50 patients for different standard deviations

Standard Deviation	19	21	23	25	27
95% CI Range*	±5.266	±5.821	± 6.375	±6.930	±7.484

*CI Range calculated using the NQuery 8, Version 8.2.7.0 program for "Confidence Interval for One Mean using Normal Distribution"

Proprietary confidential information © 2022 Boehringer Ingelheim International GmbH or one or more of its affiliated companies

8. INFORMED CONSENT, STUDY RECORDS, DATA PROTECTION, PUBLICATION POLICY, AND ADMINISTRATIVE STRUCTURE

The study will be carried out in accordance with the Medical Devices Directive (93/42/EEC) and the harmonised standards for Medical Devices (ISO 14155, current version).

The study will be carried out in compliance with the protocol, the ethical principles laid down in the Declaration of Helsinki, in accordance with the ICH Harmonized Guideline for Good Clinical Practice (GCP), relevant BI Standard Operating Procedures (SOPs), the EU directive 2001/20/EC / EU regulation 536/2014. Investigators and site staff must adhere to these principles. Deviation from the protocol, the principles of ICH GCP or applicable regulations as will be treated as "protocol deviation".

Standard medical care (prophylactic, diagnostic and therapeutic procedures) remains the responsibility of the treating physician of the patient.

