6.3 SUBJECT SETS ANALYSED

The subject analysis set used for reporting is defined as:

Entered Set (ES): those patients who were entered into the study.

The ES will be used for all types of endpoints including:

- Demographic/baseline endpoints
- Primary endpoints
- Secondary endpoints
- Safety
- •

6.5 **POOLING OF CENTRES**

There will be no statistical model specified for the primary analysis, therefore pooling of centers is not applicable.

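### The planned cough–FVC correlations show no term for diagnosis, so a diagnosis-adjusted coefficient should be reported beside each pooled one

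*SAP*

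**What the plan says.** Relating cough frequency to FVC in mL is the first secondary objective listed in protocol 2.1.1. Protocol 7.2.4 gives the analysis: "To assess the relationship between objective cough frequency and FVC (mL), correlations (spearman and Pearson) will be calculated between the following variables". Five pairs follow:

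- baseline log CC/hr with baseline FVC
- baseline log CC/hr with Week 12 FVC
- baseline log CC/hr with the 12-week change in FVC
- Week 12 log CC/hr with Week 12 FVC
- change in log CC/hr with change in FVC

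SAP 7.5.2 repeats the list and plans "Sample Spearman and Pearson correlation coefficients for the pairs of CC/hr and FVC measurements listed above", with p-values and scatter plots. Neither section mentions a stratum, covariate or partial correlation.

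On the population, protocol 3.3 states: "We will target enrolment of 25 subjects with Non IPF Pulmonary Fibrosis and 25 with IPF". SAP 6.3 names one analysis set, the Entered Set: "The ES will be used for all types of endpoints including" the primary, secondary and safety endpoints. Protocol 7.2.3 and SAP 7.4.1 promise summaries by subgroup level, in both cases for the primary endpoints. SAP 7.4.1 refers to SAP 6.4 for the list of subgroups. That section is not visible in the public document, and neither is SAP 7.6.

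**The concern.** A correlation over two groups has two parts: the relation between the variables inside each group, and the product of the differences between the group means. The second part depends on how far apart the groups lie and in what proportion they were recruited. It carries no information on whether a patient with more cough has lower FVC than another patient with the same disease.

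The plan gives some reason to keep the parts separate. Its rationale (protocol 1.3 and section 2) asks how cough in IPF resembles or differs from cough in other pulmonary fibrosis, so a group difference in cough is treated as an open question. FVC enters in mL and not as percent of predicted, so a difference between groups in age, sex or height would also feed the between-group part. Whether such differences exist is an assumption.

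What is at stake is the interpretation of one secondary objective and its nominal p-values. Protocol 7.1 makes the study exploratory, with no confirmatory test, so no formal conclusion depends on this.

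**Working it through.** **The plan's own figure.** The only precision figure is in protocol 7.5, for the mean cough count: "a two-sided 95% confidence interval for a mean will extend 7.484 from the observed mean", with N = 50 and SD 27. Check: 1.96 × 27/√50 = 7.484. The other four entries in the table (SD 19, 21, 23, 25) also reproduce: 5.266, 5.821, 6.375, 6.930. The documents give no precision figure for the correlations.

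**Inputs.** From the documents: N = 50 (protocol 7.5) and a 25/25 target (protocol 3.3). Assumed, because the documents give neither: a common within-group correlation r_w, and group mean differences dx and dy in units of the within-group SD.

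**Formula for equal groups.**

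pooled r = (r_w + dx·dy/4) / √[(1 + dx²/4)(1 + dy²/4)]

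| r_w | size of dx and dy | same direction | opposite direction |
|---|---|---|---|
| -0.30 | 0.5 | (-0.30 + 0.0625)/1.0625 = -0.22 | (-0.30 - 0.0625)/1.0625 = -0.34 |
| -0.30 | 1.0 | (-0.30 + 0.25)/1.25 = -0.04 | (-0.30 - 0.25)/1.25 = -0.44 |
| 0 | 0.5 | 0.0625/1.0625 = 0.06 | -0.06 |
| 0 | 1.0 | 0.25/1.25 = 0.20 | -0.20 |

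If only one variable differs (dx = 1, dy = 0) and r_w = 0, the pooled r is 0: no correlation is created. With r_w = -0.30 it is -0.30/√1.25 = -0.27, a slight dilution.

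**Simulation check** (20,000 trials of 25 + 25 patients, bivariate normal, two-sided p < 0.05, differences in the same direction).

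| r_w | size of dx and dy | Pearson p < 0.05 | Spearman p < 0.05 | partial Pearson p < 0.05 |
|---|---|---|---|---|
| 0 | 0 | 5% | 5% | 5% |
| 0 | 0.5 | 7% | 7% | 5% |
| 0 | 0.8 | 16% | 16% | 5% |
| 0 | 1.0 | 29% | 30% | 5% |
| -0.40 | 0 | 84% | 79% | 83% |
| -0.40 | 0.5 | 62% | 56% | 83% |
| -0.40 | 1.0 | 10% | 8% | 83% |

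The mean partial Pearson coefficient stays at about 0 or about -0.40, whatever the group differences. The partial Spearman was not simulated.

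**Cost in precision.** Adjusting for one two-level factor reduces the degrees of freedom from 48 to 47, and the critical |r| moves from 0.279 to 0.282. Separate groups of 25 are much less precise. By Fisher's z, the 95% CI around r = 0 is ± tanh(1.96/√22) = ±0.40, against ± tanh(1.96/√47) = ±0.28 at N = 50.

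**The case against.** The strongest reply is that the pooled coefficient answers the question asked. The objective concerns one cohort of patients with IPF or Non IPF pulmonary fibrosis, and protocol 7.4 describes a study with a single group. No within-disease target is stated. That stands: a reader might infer that the pooled correlation is wrong, but the documents do not support this. The error would lie in reading it as a within-disease relation.

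Four further objections also carry weight.

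- **Hidden text.** A reader might infer that no by-group correlation is planned anywhere. SAP 6.4 and 7.6 are not visible, so this cannot be said. What can be said is that no group term appears where the correlations are specified, and that the visible reference to SAP 6.4 concerns the primary endpoints.
- **The split.** A reader might take 25/25 as fixed by design. Protocol 3.3 sets it as a target, with competitive screening, and no cap per group is visible. The pooled coefficient then reflects whatever split recruitment delivers.
- **Size.** The effect needs differences in both variables of a pair. Two of the five pairs use the 12-week change in FVC, so for those the groups must differ in that change. At 0.5 SD, the shift from -0.30 to -0.22 or -0.34 is small beside the sampling interval at N = 50 (about -0.53 to -0.02).
- **Limits of the remedy.** Non IPF is itself a mixture of ILD diagnoses, and a two-level term leaves differences among them in place. One partial coefficient can also average over unlike relations in the two groups, which is why by-group coefficients belong beside it. The remedy does not address the other sampling feature, in protocol 3.3.1: "The study population will be enriched (70% of study population) for persons with clinically significant cough at the Screening Visit".

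Finally, protocol 7.2.1 has all individual data listed, so a by-group look could be recovered later. Planning it now costs little more.

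**Conclusion.** The point holds as a low-cost improvement to an exploratory analysis. As far as the visible text shows, the five cough–FVC correlations are pooled over two diagnoses recruited to a target split, with no term for diagnosis. Under equal groups, a common within-group correlation of -0.30 and differences of the same size in both variables, the pooled r lies between -0.34 and -0.22 at 0.5 SD, and between -0.44 and -0.04 at 1 SD. With no within-group relation, the artefact is about 0.06 in size at 0.5 SD and 0.20 at 1 SD.

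A reader might infer from the larger figures that the planned correlations will mislead. The documents do not support that: they give no IPF/Non IPF difference in cough or FVC, so the real effect may be negligible. The sample size, the primary endpoints and the validity of the pooled coefficient as a description of the cohort are unaffected.

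**What to change.** In SAP 7.5.2, for each of the five pairs:

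1. Keep the pooled Pearson and Spearman coefficients as planned.
2. Report next to them the partial Pearson and partial Spearman correlations adjusted for diagnosis (IPF/Non IPF).
3. Add the coefficients within each diagnosis group with 95% CIs, labelled descriptive and imprecise at about 25 patients per group.
4. Mark diagnosis by symbol in the scatter plots already planned.

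If SAP 6.4 or 7.6 already provides by-group correlations, a cross-reference from 7.5.2 would cover item 3.

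Diagnosis is recorded at screening, so no new data are needed. The partial coefficients take one PARTIAL statement in the SAS correlation procedure and one degree of freedom. The rest is a few more table rows and a plotting option.
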